### 4.6.3 Sources for overall lesion response

The tumor endpoints derivation is based on the sequence of overall lesion responses at each assessment/time point. However, the overall lesion response at a given assessment/time point will be provided from different sources as illustrated in [Table 4-4](#).

**Table 4-4 Sources for overall lesion response**

Source 1	Investigator (local radiology) reported overall lesion response (intracranial, extracranial and whole body)
Source 2	BIRC (Blinded Independent review committee) reported overall lesion response (intracranial, extracranial and whole body)

In this study, Source 1 will be used for the primary endpoint ORR, the key secondary endpoint DCR and other secondary endpoint calculations based on investigator assessment (OIRR, IDCR, TTIR, DOIR, OERR, EDCR, TTER, DOER, DOR, TTR, and PFS). Source 2 will be used to calculate OIRR, IDCR, TTIR, DOIR, OERR, EDCR, TTER, DOER, ORR, DCR, DOR, TTR,

and PFS by BIRC. In addition, OIRR, TTIR, DOIR, and IDCR are also assessed according to RANO from both Source 1 and 2.

#### 4.6.4 Kaplan-Meier estimates

To analyze time to event variables (DOIR, TTIR, DOER, TTER, DOR, TTR, OS and PFS) an estimate of the survival function will be constructed using **Kaplan-Meier (product-limit) method** as implemented in SAS PROC LIFETEST with METHOD=KM option (see example below). The TIME statement will include a variable with survival times (*survtime* in the example below) and a (right) censoring variable (*censor* in the example below) with a value of 1, representing censoring:

```
PROC LIFETEST data = dataset  
    METHOD = KM  
    CONFTYPE=LOGLOG;  
TIME survtime*censor(1);  
RUN;
```

/\* *survtime* represents variable containing event/censor times;  
*censor* represents censoring variable (1 = censored, 0 = event); \*/

Kaplan-Meier survival and failure function estimates from this procedure will be used to construct the Kaplan-Meier figures.

Median survival will be obtained along with 2-sided 95% CIs calculated from PROC LIFETEST output using the method of [Brookmeyer & Crowley, 1982](#).

Kaplan-Meier estimates with 2-sided 95% CIs at specific time points will be summarized. The time points can be expressed in weeks or in months depending on the time-to-event variable. The CIs will be constructed using Greenwood's formula [Collet, 1994, p.23] for the standard error of the Kaplan-Meier estimate.

The PROC LIFETEST statement will use the option CONFTYPE=LOGLOG. The CONFTYPE option specifies the transformation applied to the survival function to obtain the point-wise confidence intervals and the confidence intervals for the quartiles of the survival times. The LOGLOG keyword specifies the complementary log-log transformation (Collett, 1994; Lachin, 2000)  $g(x)=\log(-\log(x))$  which ensures that the point-wise confidence intervals are always within interval [0,1]. Although the LOGLOG is the default option in SAS v 9.4, it should be explicitly shown.

The Kaplan-Meier graphs will be constructed using SAS software.

#### 4.6.5 Confidence interval for response rates

The estimate of the response rates (OIRR, IDCR, OERR, EDCR ORR, DCR) will be summarized in terms of percentage rates with 95% CIs. An exact binomial confidence interval (implemented using SAS procedure FREQ with EXACT statement for one-way tables) will be calculated (Clopper and Pearson, 1934).

SAS procedure FREQ will be used to estimate the proportion of responders (binary outcome = 1 or "Yes"), along with the associated 95% (=100 × (1 – *two-sided alpha level*)) two-sided exact binomial CI. These estimates are obtained as follows:

CONFIDENTIAL - For Business Use Only

```
proc freq data = dataset;  
  table binary event /  
    binomial(  
      level = "Yes")  
      alpha = two-sided alpha level;  
  exact binomial;
```

When there are no responders, SAS does not produce a CI by default. To obtain a CI in this situation, PROC FREQ is used as specified above except changing `level="No"`. From the results of this modified procedure, the values in percent of the LCL and UCL of a 0% response rate are calculated as follows:

$$LCL_{LEVEL="Yes"} (\%) = 100\% - UCL_{LEVEL="No"} (\%)$$

$$UCL_{LEVEL="Yes"} (\%) = 100\% - LCL_{LEVEL="No"} (\%)$$

## 4.7 Safety evaluations

The text below gives more detailed instructions and rules needed for programming of the analyses described in [Section 2.8.2](#).

### 4.7.1 Multiple assessments within post-baseline visits

For all analyses regarding abnormal assessments or analyses based on worst or best post-baseline value (laboratory, ECGs, vital signs, WHO performance status), all post-baseline values will be included (scheduled, unscheduled, repeat). All unscheduled and repeat measurements will be included in listings.

#### Laboratory Data

For laboratory data, assessments can be collected from both local and central laboratory on the same date. For shift tables using CTC grades to compare baseline to the worst post-baseline value, the assessment with worst post-baseline value is used for analyses irrespective of the source. For LFT summaries, where concurrent measurements are used in the calculation of number and percentage of patients with worst post-baseline values, the assessment with worst post-baseline value is used (since worst values are based on the largest ratio of lab value to its ULN for each patient) although the worst values for the different parameters may be coming from different laboratories.

#### ECGs

For all patients, 3 ECGs are targeted to be measured at the protocol-defined (nominal) time-points. If a patient has more than one measurement at a nominal time point, the average of all available measurements associated with the nominal time point will be used for the analyses.

### 4.7.2 Baseline

As defined in [Section 2.6](#), the last available assessment before or on the date of start of study drug is defined as “baseline” value or “baseline” assessment.

#### Laboratory data

If both central and local laboratory assessments were performed on the same date and corresponding to the baseline assessment date, then the central laboratory assessment will be used for the calculation of baseline.

## ECGs

Baseline for ECG measurement is the average of all available measurements (unscheduled, if applicable) taken prior to dosing on the date associated with the last available ECG measurement before or on the date of start of study treatment. To determine whether ECG measurement was taken prior to dosing, ECG time will be compared with dosing time, if available. Unscheduled assessments will be included in the calculation of the average if ECG time is before dosing time. Study day 1 scheduled pre-dose ECGs will be considered to have been obtained prior to study drug administration if dosing time or ECG time is missing.

If a scheduled pre-dose measurement actually occurred post-dose, then the corresponding measurement will be treated and analyzed similar to an unscheduled post-dose measurement.

For unscheduled assessments on study day 1,

- if dosing time is non-missing, then the assessment is classified as post-baseline if ECG time is later than dosing time.
- if dosing time is missing, the assessment is classified as post-baseline.

The same ECG assessments will be used for both qualitative and quantitative baseline evaluations.

### 4.7.3 Laboratory Parameters

This section provides further detail on the analysis of laboratory parameters that will be listed and summarized as described in [Section 2.8.2](#).

#### Hematology

Hematologic tests include: Hemoglobin, platelets, white blood cells (WBC), red blood cells (RBC), differential (basophils, eosinophils, lymphocytes, monocytes, neutrophils (% or absolute))

The following rules will be applied to derive the WBC differential counts when only percentages are available (this is mainly for neutrophils and lymphocytes, because CTC grading is based on the absolute counts).

The method to convert the value is straightforward: for each patient, the original lab value (%) is divided by 100 and multiplied by WBC count e.g. for neutrophils (NEU):

$$\text{NEU count} = (\text{WBC count}) * (\text{NEU\%value}/100)$$

In order to derive the corresponding absolute normal range, the rule to be applied depends on the availability of the % range and the absolute range for the differential:

- If % range missing and absolute range missing, then use pre-defined normal range reported in the Merck manual

- If % absolute range NOT missing (% range is or isn't missing), then use the absolute range provided by the site
- If % range NOT missing and absolute range missing, then the % normal limits (i.e. LLN and ULN) are divided by 100 and multiplied by the corresponding normal limits of WBC count, e.g. for neutrophils NEU):  
LLN for NEU count = (LLN for WBC count)\* (LLN for NEU%value /100)  
ULN for NEU count = (ULN for WBC count)\*(ULN for NEU%value/100)

## Biochemistry

The following calculation will be applied for corrected calcium in SI unit:

Corrected calcium (mmol/L)=measured total Ca (mmol/L)+0.02 (40-serum albumin[g/L]),  
where 40 represents the average albumin level in g/L.

## 4.8 Handling of missing or partial dates

For patients not known to have died prior to the cut-off date:

- All events with start date before or on the cut-off date, and with end date missing or after the cut-off date or after the date of withdrawal of informed consent will be reported as “continuing”.
- This approach applies, in particular, to AEs and concomitant medication reports. For these events, the end date will not be imputed and therefore will not appear in the listings.

If imputation of an end date is required for a specific analysis (e.g. for a dose administration record with missing end date or last date of study drug after the cut-off date), the end date will be imputed by the minimum of death date, cut-off date and withdrawal of informed consent date for the purpose of calculating duration of exposure to study drug and dose intensity. The imputed date will be displayed and flagged in the listings.

### 4.8.1 AE date imputation

Date imputation is the creation of a new, complete date from a partial one according to an agreed and acceptable algorithm. Missing date for AE will be handled according to rules specified below. A partial date is simply an incomplete date e.g. DDOCT2001: the days are missing from this DDMMYYYY date.

Partial AE start dates, if left partial, would ultimately mean the following

It would not be possible to place the AE in time.

Therefore the treatment/dosage at the time of the event would be unknown.

Therefore the event could not be reported/summarized appropriately – if at all.

Therefore it is important to perform date imputation to ensure that as many data events are represented as correctly as possible. Of course partial and/or missing dates should *also* be caught as edit checks and passed back to the investigator for resolution.

There **will be no** attempt to impute the following:

CONFIDENTIAL - For Business Use Only

- **Missing** AE start dates
- AE start dates **missing the year**
- Partial/missing AE **end dates**

The following [Table 4-5](#) explains the abbreviations used.

**Table 4-5 AE/treatment date abbreviations**

	Day	Month	Year
Partial Adverse Event Start Date	<not used>	AEM	AEY
Treatment Start Date (TRTSTD)	<not used>	TRTM	TRTY

The following matrix [Table 4-6](#) describes the possible combinations and their associated imputations. In the light grey boxes the upper\_text indicates the imputation and the lower text the relationship of the AE start date to the treatment start date (TRTSTD).

**Table 4-6 AE partial date imputation algorithm**

	AEM MISSING	AEM < TRTM	AEM = TRTM	AEM > TRTM
AEY MISSING	NC Uncertain	NC Uncertain	NC Uncertain	NC Uncertain
AEY < TRTY	(D) Before TRTSTD	(C) Before TRTSTD	(C) Before TRTSTD	(C) Before TRTSTD
AEY = TRTY	(B) Uncertain	(C) Before TRTSTD	(B) Uncertain	(A) After TRTSTD
AEY > TRTY	(E) After TRTSTD	(A) After TRTSTD	(A) After TRTSTD	(A) After TRTSTD

The following [Table 4-7](#) is the legend to the above table.

**Table 4-7 AE/treatment date relationship and imputation legend**

Relationship	
Before TRTSTD	Indicates AE start date prior to Treatment Start Date
After TRTSTD	Indicates AE start date after Treatment Start Date
Uncertain	Insufficient to determine the relationship of AE start date to Treatment Start Date
Imputation Calculation	
NC / Blank	No convention/imputation
( A )	01MONYYYY
( B )	TRTSTD+1
( C )	15MONYYYY
( D )	01JULYYYY
( E )	01JANYYYY

The following [Table 4-8](#) gives a few examples.

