8.1.1 Definitions and reporting

An adverse event is defined as the appearance of (or worsening of any pre-existing) undesirable sign(s), symptom(s), or medical condition(s) that occur after patient's signed informed consent has been obtained.

For patients whose ALK status is unknown and who sign the molecular pre-screening ICF, AEs which occur after signature of this consent will only be captured if they meet the definition of serious as outlined in [Section 8.2](#) and are reported to be causally related to study procedures (e.g. an invasive procedure such as biopsy). Once the main study ICF is signed, all AEs per the descriptions below will be captured in the Adverse Event eCRF. Abnormal laboratory values or test results occurring after informed consent constitute adverse events only if they induce clinical signs or symptoms, are considered clinically significant, require therapy (e.g., hematologic abnormality that requires transfusion or hematological stem cell support), or require changes in study medication(s).

Adverse events that begin or worsen after informed consent should be recorded in the Adverse Events eCRF. Conditions that were already present at the time of informed consent should be recorded in the Medical History page of the patient's eCRF. Adverse event monitoring should be continued for at least 30 days (or 5 half-lives, whichever is longer) following the last dose of study treatment. Adverse events (including lab abnormalities that constitute AEs) should be described using a diagnosis whenever possible, rather than individual underlying signs and symptoms. When a clear diagnosis cannot be identified, each sign or symptom should be reported as a separate Adverse Event.

Adverse events will be assessed according to the Common Terminology Criteria for Adverse Events (CTCAE) version 4.03 (dated 14 June 2010). If CTCAE grading does not exist for an adverse event, the severity of mild, moderate, severe, and life-threatening, corresponding to Grades 1 - 4, will be used. CTCAE Grade 5 (death) will not be used in this study but is collected as seriousness criteria; rather, information about deaths will be collected through a Death eCRF.

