### Concomitant therapy

Concomitant therapies are defined as any medications (excluding study drug, prior antineoplastic treatments and blood transfusions), surgeries or procedures (including physical therapy) administered in the study and are recorded in the Prior and Concomitant Medications and the Surgical and Medical Procedures eCRF, respectively.

Concomitant medications will be coded using the WHO Drug Reference Listing (WHO DRL) dictionary that employs the WHO Anatomical Therapeutic Chemical (WHO ATC) classification system. Surgeries or procedures will be coded using the Medical Dictionary for Regulatory Activities (MedDRA) terminology. All summaries will be tabulated using frequency counts and percentages by study arm.

Concomitant therapies will be summarized by ATC class and preferred term by study arm and for all patients. These summaries will include: 1) medications starting on or after the start of study drug but starting no later than 30 days after last dose of study drug; and 2) medications starting prior to the start of study drug but continuing after the start of study drug.

All concomitant therapies and surgeries and medical procedures will be listed. Any concomitant therapies starting and ending prior to the start of study drug or starting more than 30 days after the last date of study drug will be flagged in the listings.

CONFIDENTIAL - For Business Use Only

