### Observation periods for the analyses

CONFIDENTIAL - For Business Use Only

The overall observation period will be divided into three mutually exclusive segments:

- Pre-treatment period: from day of patient's informed consent to the day before first dose of study drug
- On-treatment period:
  - For discontinued patients, from day of first dose of study drug to 30 days after last dose of study drug
  - For ongoing patients, from day of first dose of study drug to the data cut-off date
- Post-treatment period: starting at day 31 after last dose of study drug

The safety summary tables will include only assessments collected during the on-treatment period.

For select items, shift tables or change from baseline summaries generated for laboratory, ECG, vital signs and change score (WHO PS) generation may use data from pre-treatment period for baseline calculations.

All data, regardless of observation period, will be listed and assessments collected during the pre-treatment and post-treatment period will be flagged in all the listings.

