#### 4.8.2 Concomitant medication date imputation

The imputation of the start date of concomitant medication will follow the same conventions as for AE date. Partial concomitant medication end dates will not be imputed.

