#### 4.8.4 Incomplete date for anti-neoplastic therapies

##### Prior therapies

###### Start date:

The same rule which is applied to the imputation of AE/concomitant medication start date will be used with the exception that for scenario (B) will be replaced to be 'start date of study drug -1'.

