###### End date:

Imputed date = min (start date of study drug, last day of the month), if day is missing;

Imputed date = min (start date of study drug, 31DEC), if month and day are missing.

If the end date is not missing and the imputed start date is after the end date, use the end date as the imputed start date.

If both the start date and the end date are imputed and if the imputed start date is after the imputed end date, use the imputed end date as the imputation for the start date.

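### Rule (B) for partial start dates ignores a known end date, so adverse events and drugs that ended before first dose can be counted as starting on treatment

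*SAP*

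**What the plan says.** SAP 4.8.1 imputes a partial adverse-event (AE) start date from two things only: its recorded month and year, and the month and year of first dose. Table 4-6 is a four-by-four matrix. Two of its 16 cells lead to rule (B): start year equal to treatment year, with the month either missing or equal to the treatment month. Table 4-7 defines the label on these cells as "Insufficient to determine the relationship of AE start date to Treatment Start Date" and sets the imputed start to first dose plus one day.

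For concomitant medication, SAP 4.8.2 states: "The imputation of the start date of concomitant medication will follow the same conventions as for AE date". Both sections mention end dates only to say that partial or missing ones are not imputed.

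SAP 4.8.4 treats prior antineoplastic therapy differently. Rule (B) is changed there ("with the exception that for scenario (B) will be replaced to be" the day before study drug), and there is an explicit end-date check: "If the end date is not missing and the imputed start date is after the end date, use the end date" as the start.

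The imputed start date then decides what is tabulated:

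- SAP 2.8.2 defines the on-treatment period as "For discontinued patients, from day of first dose of study drug to 30 days after last dose of study drug", and adds: "The safety summary tables will include only assessments collected during the on-treatment period".
- SAP 2.6 selects its first group of concomitant drugs by start date alone: "medications starting on or after the start of study drug but starting no later than 30 days after last dose of study drug". The second group is drugs that began before study drug and continued after it.

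**The concern.** Rule (B) is meant for records that cannot be placed before or after first dose. A complete end date before first dose settles that question, but the rule does not look at it. The result is a start date later than the end date, and a pre-treatment record counted as on treatment.

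Such records can be expected. Protocol 8.1.1 collects AEs once "signed informed consent has been obtained", and Protocol 6.4 collects medications given in the 28 days before first dose. Protocol 5.3 also requires certain drugs, such as enzyme-inducing anticonvulsants, to be stopped at least a week before ceritinib. A drug stopped as required, with a partial start date in a rule (B) cell, would be tabulated as begun the day after first dose. That would look like prohibited use on study.

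The listing flags do not rescue this. SAP 2.6 flags drugs that both start and end before study drug, and SAP 2.8.2 flags pre-treatment data. An imputed post-dose start takes the record out of both.

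**Working it through.** **1. Reproduce the plan's own examples.** The Table 4-6 matrix with the Table 4-7 legend was programmed and run on all seven rows of Table 4-8 (first dose 20OCT2001). All seven agree in rule and date. The two rule (B) rows, ddmmm2001 and ddOCT2001, both give 21OCT2001.

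**2. Add a known end date before first dose.** The check from SAP 4.8.4 amounts to: start = min(imputed start, known end date).

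| Partial start | Known end | Rule | Start as planned | Start minus end | Period as planned | Start with check | Period with check |
|---|---|---|---|---|---|---|---|
| ddOCT2001 | 15OCT2001 | B | 21OCT2001 | +6 days | on-treatment | 15OCT2001 | pre-treatment |
| ddmmm2001 | 05OCT2001 | B | 21OCT2001 | +16 days | on-treatment | 05OCT2001 | pre-treatment |
| ddSEP2001 | 10SEP2001 | C | 15SEP2001 | +5 days | pre-treatment | 10SEP2001 | pre-treatment |

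The third row shows the limit of the problem. Rule (C) can also put a start after an end, but the record stays pre-treatment. Rule (D) likewise places the start before first dose. Rules (A) and (E) apply only when the recorded month or year is already after that of first dose. Only rule (B) moves a record that ended before treatment into the on-treatment period.

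**3. How much of the pre-dose window falls in rule (B) cells.** Assumption: first-dose dates are spread evenly over the calendar. With first dose on day d of a month, min(d − 1, 28) of the preceding 28 days lie in the same month.

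- 31-day month: (0 + 1 + … + 28) + 28 + 28 = 462
- 30-day month: 406 + 28 = 434
- 28-day February: 0 + 1 + … + 27 = 378
- Ordinary year: (7 × 462 + 4 × 434 + 378) / (365 × 28) = 5348 / 10220 = 52%

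For the same calendar year (relevant when the month is also missing), only first doses on 1 to 28 January lose days: 28 + 27 + … + 1 = 406, and 1 − 406/10220 = 96%. Day-by-day enumeration over 2015 to 2017 gives the same 52% and 96%.

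These shares describe exposure to the rule. They do not say how many such records have a partial start date or an end before first dose.

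**4. Weight of one misclassified patient.** Enrolment is from the Amendment 6 rationale: 42, 40, 12, 44 and 18 in Arms 1 to 5, 156 in all. Assumption: all were dosed and so belong to the Safety Set. One patient moves an incidence by 100/n percentage points:

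- Overall: 100/156 = 0.64
- Arms 1, 2 and 4: 100/42 = 2.4, 100/40 = 2.5, 100/44 = 2.3
- Arm 5: 100/18 = 5.6
- Arm 3: 100/12 = 8.3

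**The case against.** The strongest defence is that placing an undetermined start on treatment is the conservative choice for safety, and that any error overcounts AEs. As a default this stands. It does not cover a record whose end date already determines the answer, and the check leaves the default in place everywhere else.

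The second defence is that few records will be affected. SAP 4.8.1 says partial dates should also be queried back to the investigator, and Protocol 9.3 and 9.4 describe validation checks and electronic queries. An affected record must still have a partial start after queries, fall in one of two cells, and have an end date before first dose. This stands as a limit on size, but queries do not correct what remains.

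Third, all safety data are listed, so a start after its end could be noticed. It would still be in the summary tables.

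A reader might infer three stronger claims that the documents do not support:

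- *Half of screening AEs with a missing start day are wrongly moved.* The 52% is calendar overlap. Events still ongoing at first dose are treated as the plan intends, and the share that ended earlier is unknown.
- *Every partial start date is moved to the day after first dose.* Rule (B) fills two of 16 cells.
- *Steroids or anticonvulsants begun earlier in the year and still taken at first dose are wrongly counted.* They belong in the concomitant summary through the second group in SAP 2.6, and an end-date check does not alter them.

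**Conclusion.** The point holds for a narrow class of records: partial start date in a rule (B) cell, and a complete end date before first dose. For these the stated rule gives an impossible date sequence and the wrong observation period, in the AE tables and in the first concomitant-medication group.

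The number of such records is not given and cannot be derived from the documents. Each patient wrongly counted for a given term costs 0.64 points overall, but 5.6 in Arm 5 and 8.3 in Arm 3. The by-arm safety tables are therefore where a handful of records would show. This rests on the enrolment counts equalling the Safety Set, and on AEs being assigned to a period by start date. SAP 4.8.1 implies the latter when it says that an event with a partial start could not be placed in time.

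Response endpoints, including ORR and DCR, do not use these dates. This is a modest, avoidable error in the safety reporting and no threat to the trial's efficacy conclusions.

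**What to change.** Carry the SAP 4.8.4 sentence into 4.8.1 and 4.8.2: "If the end date is not missing and the imputed start date is after the end date, use the end date" as the imputed start. A record that ended before first dose then becomes pre-treatment. One that ended on the day of first dose gets that day as its start and stays on treatment.

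For partial end dates a separate rule is needed. It is not in 4.8.4, and 4.8.1 and 4.8.2 do not impute end dates. Suggested wording: where the last possible day of a partial end date is before first dose, classify the record as pre-treatment. For example, with first dose on 20OCT2001 and end ddSEP2001, the last possible day is 30SEP2001, so the record is pre-treatment. No end date has to be imputed for this.

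Keep rule (B) as the conservative default in all other cases. The cost is two sentences in the SAP and a few lines of programming, with no new data collection.
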